8.10 Study Exit or Premature Withdrawal

Subjects will be formally exited from the study through the completion of the Study Exit CRF at the time of study completion, provided the subject has not experienced an AE directly attributable to the study device or procedure that is ongoing and unstable and/or unexplained.

Subjects may be prematurely terminated or withdrawn from the study for the following reasons:

- Not eligible for treatment
- Subject starts a medication or treatment that, in the opinion of the investigator, may skew study results
- Lost to follow-up (following 3 documented attempts to reach subject)
- In the investigator's opinion, it is not in the best interest of the subject to continue study participation
- Voluntary withdrawal, meaning that the subject voluntarily chooses not to participate in the study

All subjects enrolled (including those prematurely withdrawn) shall be accounted for and documented.

CANDESANT BIOMEDICAL	CLINICAL STUDY PROTOCOL SAHARA STUDY	Document #: CB-CLP-001 Revision: E
-------------------------	---	---------------------------------------

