By these two studies, the N-SWEAT device has demonstrated a favorable safety profile. No SAEs have been reported to date. Three (3) total device-related events that occurred in this cumulative data set (2 mild and 1 moderate) were all skin reactions that were treated topically, and all resolved without sequelae. Moreover, data on the subjects' condition after treatment including HDSS and QoL assessments are also consistent; subjects largely feel like their condition is improved.

These findings establish acute safety and suggest effectiveness sufficiently to warrant the initiation of this pivotal trial; the SAHARA Study is intended to confirm safety and further demonstrate efficacy of the N-SWEAT Patch in a larger multi-center representative population.

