8.7.5 Subject Care and Medications

Subjects will be provided with instructions for post-treatment care. They will be instructed to rinse the area with water or cleanse with soap and water if they feel any discomfort. Deodorant will be provided for use during study participation.

CANDESANT BIOMEDICAL	CLINICAL STUDY PROTOCOL SAHARA STUDY	Document #: CB-CLP-001 Revision: E
-------------------------	---	---------------------------------------

Subjects may take over-the-counter pain medication as needed following treatment. Acetaminophen is recommended for pain control. Prescription strength pain medication is not expected to be necessary.

Subjects must refrain from using over-the-counter or prescription, prescription-strength, or clinical strength topical aluminum compounds or antiperspirants for the duration of study participation. An approved deodorant (without antiperspirant) will be provided at screening for convenience. Other deodorants without antiperspirant may be allowed; however, they must be approved by the investigator. Subjects must also refrain from using topical steroids or hair removal creams on the treatment areas.

Subjects must refrain from taking anticholinergic medications, beta blockers, calcium channel blockers, other systemic treatments, or medications that are known to cause heavy sweating during the study. If one or more of these medications or treatments are required, and in the opinion of the investigator would compromise study results, the subject will be followed for safety only. All relevant medications taken will be documented.

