10.2 Adverse Event Review by Investigator

Each AE will be assessed by the investigator as to its relationship and level of relatedness to the device and/or procedure. In addition, the investigator will identify the date of onset, any required treatment or intervention, severity, and duration. All AEs will be monitored until they are adequately resolved, stabilized and/or explained.

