10.3 Adverse Event Reporting

All AEs and ADEs will be recorded by the investigator or designee on the case report forms (CRFs) provided. The investigator at each site is ultimately responsible for reporting AEs to the IRB according to IRB requirements and to the sponsor in accordance with the Investigational Plan and applicable FDA regulations. The site will be instructed to report all AEs considered moderate or severe and all local skin reactions to Candesant within 5 working days of the identification of the AE.

If an Adverse Event is considered a local skin reaction within the treated area, photos are required to be submitted as part of the Adverse Event Report. Submitted photos should show documentation of AE onset, AE progression and/or healing and AE

CANDESANT BIOMEDICAL	CLINICAL STUDY PROTOCOL SAHARA STUDY	Document #: CB-CLP-001 Revision: E
-------------------------	---	---------------------------------------

resolution (if applicable). Photos are to be taken with a high-resolution camera with the arm in the standardized treatment position and adequately illuminated. Photos are to be marked with Subject ID, date and subject side (i.e. Right or Left). Photos are to be taken with a measurement calibration reference visible.

AEs or complications meeting the definition for UADEs must be reported by the investigator to the sponsor as soon as possible, but in no event, later than 10 working days after the investigator first learns of the event. The sponsor will conduct an evaluation of any reported UADEs and will report the results of this evaluation to the FDA, IRBs, and participating investigators within 10 working days after first receiving notice of the event.

Descriptive and photographic data will be recorded and maintained on file for all AEs regardless of severity or device-relatedness. All observed local skin reactions will also be recorded.

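### Protocol 8.7.5 and 8.10 give inconsistent dispositions when a subject starts a medication that could affect results, and 8.10 allows scheduled follow-up to end

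*Protocol*

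**What the plan says.** Protocol 8.7.5 restricts medications in two consecutive paragraphs. The first deals with antiperspirants and products applied to the axilla, and ends: "Subjects must also refrain from using topical steroids or hair removal creams on the treatment areas". The second bars anticholinergics, beta blockers, calcium channel blockers and other systemic treatments. It then says what happens if one of them is needed and "in the opinion of the investigator would compromise study results, the subject will be followed for safety only".

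Protocol 8.10 opens its list of exit grounds with "Subjects may be prematurely terminated or withdrawn from the study for the following reasons". One ground is "Subject starts a medication or treatment that, in the opinion of the investigator, may skew study results". It does not mention safety-only follow-up. Formal exit is allowed "provided the subject has not experienced an AE directly attributable to the study device or procedure that is ongoing and unstable and/or unexplained", but that condition is written for exit at study completion and is not repeated for premature withdrawal.

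Two other sections bear on what happens to an adverse event. Protocol 10.2 says "All AEs will be monitored until they are adequately resolved, stabilized and/or explained", with no exception for withdrawn subjects. For local skin reactions, Protocol 10.3 adds "Submitted photos should show documentation of AE onset, AE progression and/or healing".

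**The concern.** The two sections rest on almost the same investigator judgment, that a medication interferes with the results. One keeps the subject under observation and the other permits removal.

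This matters here because the restricted list overlaps with products that might be used for a skin reaction. Protocol 3.3 reports that the three device-related events in the earlier studies "were all skin reactions that were treated topically, and all resolved without sequelae". Protocol Table 6 describes severe events as generally needing systemic drug therapy or other treatment. A medication started after treatment may therefore be a consequence of a post-treatment event. If the medication leads to exit, leaving follow-up becomes related to outcome, and possibly to arm. Scheduled safety observation and the week-4 efficacy value could both be missing for reasons that are not random.

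**Working it through.** The point rests on no reported figure, so the check is a comparison of the texts.

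**Step 1. The two rules side by side.**

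| | Protocol 8.7.5 | Protocol 8.10 |
|---|---|---|
| Which medications | Those restricted in the section; unclear whether topical steroids in the preceding paragraph are included | Any medication or treatment |
| Threshold | Required, and would compromise results | Started, and may skew results |
| Who judges | Investigator | Investigator |
| Disposition | Safety-only follow-up | Premature termination or withdrawal |
| Force | Mandatory | Permissive |
| Reference to the other section | None | None |

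The triggers overlap without being identical. A restricted systemic drug that the investigator thinks would compromise results satisfies both. A topical steroid on the axilla clearly satisfies 8.10 if the investigator thinks it may skew results; whether it falls under 8.7.5 depends on how far back the wording reaches.

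**Step 2. What survives an 8.10 exit.** An adverse event already identified must still be monitored (Protocol 10.2), and a skin reaction must be photographed (Protocol 10.3). The subject stays in the safety population, which is everyone randomized plus the roll-in cohort (SAP 6.3), so recorded events remain counted.

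**Step 3. What does not clearly survive.** Sections 10.2 and 10.3 attach to an event that has been found; they do not preserve the schedule that finds one. Local skin assessments are tied to clinic visits (Protocol Table 4, Appendix B), and the schedule runs to week 12 (Protocol 8.8). Weekly HDSS and QoL surveys begin at week 1. A subject exited just after the week-1 survey would miss the surveys for weeks 2 to 12, that is 12 − 1 = 11 of 12, plus the week-2 call and the evaluations at weeks 4, 6, 8, 10 and 12. Late events are not remote in the plan's own terms: Protocol 11.2 lists scarring and discoloration among the risks, and the first stopping rule in Protocol 11.5 refers to erythema developing more than 7 days after treatment.

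**Step 4. Effect on the primary analysis.** SAP 11.1 runs the stratified CMH test in the full analysis set, which SAP 6.4 defines as ITT subjects with evaluable data for the endpoint. Exit before week 4 with no week-4 HDSS removes the subject from that test. The subject returns only in the imputation analyses of SAP 9. The planned allowance is 55 − 50 = 5 subjects per arm (SAP 4), so a handful of exits in one arm would use it. Section 8.7.5 is not fully protective either, because it does not define safety-only follow-up or say whether HDSS collection continues.

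**Step 5. Number affected.** The documents do not name the topical products used earlier, say how often an investigator would judge a product to affect results, or say how often that judgment would lead to exit. No estimate can be built from them.

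**The case against.** The best defence is that a specific mandatory rule and a general permissive list can be read together: 8.7.5 governs restricted medications, 8.10 says only that a subject may be withdrawn, and the sole defect is a missing cross-reference. That shows the sections can be reconciled. It does not show that they have been, and a site following 8.10 alone would still comply.

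A reader might infer more: that a subject medicated for a skin reaction loses the follow-up showing how that reaction ended, so that time to resolution goes unrecorded. The documents do not support this. Protocol 10.2 requires the open event to be followed and 10.3 requires photographs; losing that outcome would breach 10.2.

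A reader might also try to size the problem from the earlier studies: 3 device-related events in 12 + 8 = 20 treated subjects is 15% (Wilson 95% interval 5.2% to 36.0%), or about 10 of 10 + 55 = 65 N-SWEAT subjects (3.4 to 23.4). That counts expected skin reactions, not withdrawals. It assumes one event per subject, ignores that four of the 12 were re-treated, and would equal exits only if every reaction were treated with a restricted product, judged to affect results, and followed by a discretionary decision to withdraw.

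Finally, missing week-4 values are addressed by the best-case, worst-case and tipping-point analyses in SAP 9. This stands as far as it goes, but those analyses show sensitivity to missing data; they do not recover an observation that could have been collected.

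**Conclusion.** The inconsistency is real and should be corrected. For overlapping triggers, 8.7.5 requires safety-only follow-up while 8.10 permits termination, and the position of topical steroids is unclear.

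The consequence is bounded. The outcome of an open adverse event remains covered. What is exposed is scheduled observation through week 12 for new or late events, and the week-4 HDSS of anyone exited before that visit. The size cannot be given. Any loss depends on three things the documents do not quantify: use of a medication that meets the 8.10 wording, an investigator's judgment that it may affect results, and a decision to withdraw. That exits would fall mainly in the active arm is plausible but is not shown by the documents.

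**What to change.** Reconcile the two sections as follows.

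- **Protocol 8.10:** remove the medication bullet as a reason to end follow-up. State that monitoring under 10.2 continues after any premature withdrawal, as far as consent allows.
- **Protocol 8.7.5:** state that starting any restricted medication, topical steroids included, does not end data collection. Scheduled safety assessments and HDSS/QoL collection, including the week-4 visit, continue unless the subject withdraws consent or another 8.10 ground applies, such as the investigator's judgment of the subject's best interest.
- **Records and analysis:** record the medication and its start date, and consider it in the Per-Protocol review that SAP 6.5 places before data lock and unblinding.

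The cost is a wording amendment, processed under Protocol 12.5. The downside is that some HDSS values will be collected after a restricted medication; they can be flagged and, where the review so decides, excluded from the Per-Protocol set. The change concerns data collection only and takes no position on how a reaction is treated.

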9. STATISTICAL METHODS

9.1 General Statistical Analysis Methods

Categorical variables will be summarized by counts and percentages. Continuous variables will be summarized by n, mean, standard deviation, minimum, median and maximum.

When the arithmetic mean is found not to be an appropriate measure of central tendency, alternative statistics will be considered (e.g. median). When the distribution of a variable does not support the use of parametric statistics, nonparametric approaches or data transformations may be implemented. If data transformations are used, they will be specified in the final clinical report.

9.2 Study Design, Randomization and Blinding

The Sahara Study is a prospective, multi-center, randomized, blinded, pivotal study to evaluate the safety and effectiveness of the N-SWEAT Patch.

Subjects with primary axillary hyperhidrosis or excessive sweating (defined by a score of 3 or 4 on the HDSS), who have provided informed consent and have met the study eligibility criteria, will participate. Up to 120 adult subjects will be enrolled. The first 10 subjects will be treated with the N-SWEAT patch and constitute the roll-in cohort and up to 110 subjects will be randomized to 1 of 2 treatment groups in a 1:1 ratio to receive a single administration of the N-SWEAT Patch or a sham control patch. The randomization will be blocked by investigational center and stratified by HDSS 3 vs. 4 at baseline. Up to 10 additional subjects may be enrolled to account for loss to follow up or other missing and critical data.

Randomized subjects will be blinded to their treatment assignment. Site personnel administering the treatment will observe the treatment effect and the disposal process and may be unblinded as a result of their observations. This person will not conduct the follow-up assessments and will not reveal the assumed treatment assignment to the subject, other site personnel, or the investigator at any time during the study follow-up period. Study subjects and study staff will be instructed not to discuss assumptions about the treatment received.

The sponsor will identify those who need to be unblinded in order to conduct the study. All others at the sponsor will remain blinded.

9.3 Sample Size and Power Considerations

The primary effectiveness evaluation is driving the randomized sample size for the trial. The maximum of two scenarios considered required 50 evaluable per randomized group at 4 weeks of follow-up. Increasing that number for up to 10% attrition requires 55 randomized subjects per group or 110 randomized subjects. This number provides at least 80% power for the primary efficacy objective.

CANDESANT BIOMEDICAL	CLINICAL STUDY PROTOCOL SAHARA STUDY	Document #: CB-CLP-001 Revision: E
-------------------------	---	---------------------------------------

The trial is also designed to also enroll a roll-in cohort of N=10 treatment subjects at one investigational center prior to randomizing any subjects in the trial.

9.4 Study Success

The Sahara study will be deemed a success with a statistically significantly higher proportion of patients with HDSS score of 1 or 2 at 4 weeks post-treatment in subjects randomized to treatment vs. sham (primary effectiveness endpoint) accompanied by an acceptable safety profile.

9.5 Analysis Sets / Populations

9.5.1 Roll-in Cohort

The roll-in cohort is an initial cohort of N=10 treatment subjects enrolled at one investigational site to provide FDA with an initial assessment for safety of the device. Efficacy endpoints for roll-in subjects will be restricted to summary statistics and reported separately for roll-in subjects.

9.5.2 Intent-to-Treat Population

The intent-to-treat (ITT) population will include all randomized patients assigned to treatment. In this population, treatment will be based on the treatment to which patients were randomly assigned regardless of which treatment they actually received.

9.5.3 Safety Population

The safety population is the ITT population plus the roll-in cohort.

9.5.4 Modified Intent-to-Treat and Full Analysis Set

The modified intent to treat (mITT) will include all randomized patients in the ITT population who were exposed to randomized treatment. The full-analysis set (FAS) is those mITT subjects that have evaluable data for the endpoint.

The mITT population, like the ITT population, will include all randomized patients assigned to treatment regardless of which treatment they actually received. However, unlike the ITT population, the mITT population excludes patients who are randomized but fail to initiate treatment (treatment or control patch).

9.5.5 Per-Protocol Set

The Per Protocol Set (PP) will include all randomized subjects in the FAS who did not have any major protocol violations. Definitions of major and minor protocol violations will be included in the Statistical Analysis Plan (SAP) prior to data lock and unblinding of the person(s) determining major or minor status. If no subjects are excluded from the PP, the PP will not be required. The PP will be used for supporting analyses of efficacy data.

CANDESANT BIOMEDICAL	CLINICAL STUDY PROTOCOL SAHARA STUDY	Document #: CB-CLP-001 Revision: E
-------------------------	---	---------------------------------------

9.6 Timing of Analyses

Safety for the Roll-in cohort will be summarized when at least 2 weeks of follow-up is available on the last enrolled roll-in subject.

Once all subjects complete 4 weeks of follow-up, the data will be summarized for evaluation of the endpoints. Lastly, the data will be summarized when all subjects complete 12 weeks of follow-up.

9.7 Assessment of Comparability of Randomized Groups and Evaluation for Pooling

9.7.1 Demographics / Baseline Characteristics and Protocol Administration

Patient disposition will be listed and summarized for the mITT, ITT and roll-in data sets by treatment group. Protocol deviations will be collected and summarized by randomized group in the ITT population and roll-in group.

Demographics (age, gender, race/ethnicity) and baseline characteristics (HDSS, GSP, Fitzpatrick skin type, and BMI) will be summarized by treatment group for ITT, mITT and roll-in groups.

The randomized groups will be compared at time of randomization for the important demographics and baseline characteristics specified. Should additional important baseline parameters be identified prior to the analysis, they will be evaluated in the same manner. Any of the variables that are significant at a two-sided $\alpha=0.05$ will be evaluated as covariates or strata variables in the primary effectiveness analysis or as an additional or supporting analysis to the primary effectiveness endpoint and if desired, secondary/observational endpoints as well. Continuous variables will be evaluated both as stratification variables by dichotomizing the subjects into two groups based on the median or other appropriate value and as a continuous variable in the statistical models. Logistic regression analysis may be used for the primary efficacy endpoint should it be desirable to evaluate multiple covariates simultaneously in a statistical model.

9.7.2 Treatment Characteristics

At a minimum, the duration of patch placement, pain level during treatment and cleaning will be summarized by randomized group for the mITT and roll-in population.

9.7.3 Evaluation for Pooling

Pooling of the investigational sites will be evaluated for the primary efficacy endpoint. Investigational centers with less than 10 randomized subjects will be combined for this purpose. The Breslow-Day test will be used to assess the treatment by site interaction and if statistically significant at $p<0.15$, an overall response rate will be evaluated at 4-weeks using CMH test stratified by site. If not statistically significant, the data will be pooled for analysis.

CANDESANT BIOMEDICAL	CLINICAL STUDY PROTOCOL SAHARA STUDY	Document #: CB-CLP-001 Revision: E
-------------------------	---	---------------------------------------

9.8 Handling of Missing Data for the Primary Efficacy Endpoint

A sensitivity analysis to the missing data in the mITT sample will be conducted for the primary efficacy endpoint. The sensitivity analysis will include a best case, worst case and tipping point analysis. The best case analysis will impute successes for subjects randomized to treatment with missing data and failures for subjects randomized to sham with missing data. The worst case analysis will impute failures for subjects randomized to treatment with missing data and success for subjects randomized to sham with missing data. The tipping point analysis completes the matrix of imputations possible between the best case and worst analysis to determine where statistical significance is maintained or lost. If the worst case analysis maintains statistical significance, the tipping point analysis is not necessary.

9.9 Primary Safety Analysis

Subjects Included in Analysis: All subjects in the Safety Cohort.

Endpoint(s): Local skin reactions and adverse events.

Hypothesis: A single hypothesis test associated with a specific safety endpoint is not being proposed for the primary safety outcome. Rather, the local skin reaction and adverse event profile in total will be reviewed for acceptability.

Primary Statistical Analysis: Number and percent of subjects affected by each event or reaction will be summarized. Subgroups of events/reactions will also be summarized and include but are not limited to serious events, those related to the treatment, and those that are both serious and related to the treatment.

